(Appendix)

## STUDY INFORMATION

Title	Vyndaqel Capsules Special Investigation -Investigation on patients with transthyretin amyloid cardiomyopathy-
Protocol number	B3461064
Protocol version identifier	8
Date	24 October 2023
Active substance	Tafamidis meglumine, Tafamidis
Medicinal product	Vyndaqel® Capsules 20 mg, Vynmac® Capsules 61 mg
Research question and objectives	
To comprehend information on the long-term safety (e.g., onset status of adverse reactions), etc. of patients who are treated with Vyndaqel Capsules 20 mg (hereinafter referred to as Vyndaqel) for the treatment of transthyretin amyloid cardiomyopathy. When Vynmac Capsules 61 mg (hereinafter referred to as Vynmac) is used, conduct the study to grasp information on safety (e.g., onset status of adverse reactions), etc. during the observation period.
 
[Conditions for approval for Vyndaqel] Because the number of study participants in Japan is very limited, the background information of patients using this drug* should be grasped by conducting a use-result survey in all patients while the data on a certain number of patients is accumulated after marketing and data on the safety and effectiveness of this drug should be collected early to take measures necessary for proper use of this drug.
 
*: Vyndaqel
 
[Conditions for approval for Vynmac] Because the number of study participants in Japan is very limited, the background information of patients using this drug** or Vyndaqel Capsules 20 mg should be grasped by conducting a use-result survey in all patients while the data on

PFIZER CONFIDENTIAL

	
a certain number of patients is accumulated after marketing and data on the safety and effectiveness of this drug or Vyndaqel Capsules 20 mg should be collected early to take measures necessary for proper use of this drug.
 
** : Vynmac

Author	
PPD
 
PPD

## 2. LIST OF ABBREVIATIONS

Abbreviation	Definition
ATTR-CM	transthyretin amyloid cardiomyopathy
BNP	brain natriuretic peptide
EDC	electronic data capture
N/A	not applicable
NT-pro BNP	N-terminal pro-hormone brain natriuretic peptide
SAP	statistical analysis plan
TTR	transthyretin
TTR-FAP	transthyretin-type familial amyloid polyneuropathy

### 3. RESPONSIBLE PARTIES

The Japan Good Post-marketing Study Practice officer

### 4. AMENDMENTS AND UPDATES

Amendment number	Date	Type of amendment (substantial or administrative)	Protocol section(s) changed	Summary of amendment(s)	Reason
Amended 7	24 October 2023	Substantial	4, 6, 8.2.4, 8.2.5, 8.2.6, 8.3, 8.3.1, 8.6.4, 8.6.7, 8.6.9, 9.3, 12	Deletion of the descriptions regarding registration not requiring preparation of case report forms.	Because registration not requiring preparation of case report forms was completed based on Q&A 5 in the Administrative Notice dated 10 August 2023, and the text was reviewed and corrected.
Amended 6	17 November 2022	Administrative	5, 6, 8.2.2, 8.2.5.1, 8.3, 8.6.5.2, 8.6.9, 8.7, 8.9, 9, 9.4, 10.1, 10.4.1, 10.4.2, 10.4.3, 12, 16	Change of the contact information, Change of the reference to the organizational structure, Minor corrections.	Because the text was reviewed and corrected in association with the change of the contact information and the change of the reference to the organizational structure.
Amended 5	12 January 2022	Administrative	STUDY INFORMATION, 13, 17.1	Change of the Department Name, Change of the scope of work contracted.	Because of organization changes, and because of scope of work contracted was updated.
Amended 4	18 October 2021	Substantial	6, 7, 7.1, 8.1, 8.2.1, 8.2.5.1, 8.3, 8.3.1, 8.3.2, 8.3.6, 8.3.8, 8.5, 8.6.6, 8.6.9, 8.7, 10.1, 10.2, 10.3, 10.4.3, 13, 14, 15, 17.2, 19, 20	Add that information on Vynmac treatment will be also collected to evaluate safety. Minor corrections.	Because the study will be continued when Vynmac is used to collect information on Vynmac treatment during the observation period, and because the text was reviewed and corrected.
Amended 3	24 March 2021	Substantial	8.2.4, 8.2.5.1, 8.2.6, 8.3, 8.3.1, 8.6.4, 8.6.7, 8.6.9	Change of the registration period in association with shifting to patient registration only. Add patients to be registered,	Because of shifting to patient registration only

PFIZER CONFIDENTIAL

				registration method, etc.	
Amended 2	05 July 2019	Administrative	8.6.1	Add the data correction method	Because the data correcting method was added.
			10	Add sections	Because the Safety Reporting Language provided as attachment was merged.
Amended 1	25 April 2019	Administrative	8.2.4	Change of the registration period	Because the timing to start the registration period was adjusted to the timing to start this study
Final	29 March 2019	N/A	N/A	N/A	N/A

## 5. MILESTONES

Milestone	Planned date
Start of data collection (start date of observation for the first subject)	March 2019
Start of data collection (date of registration of the first subject)	03 October 2019
End of data collection (end date of observation for the last subject)	September 2023
End of data collection (date of release of the database)	November 2024
Final study report	April 2025

## 6. RATIONALE AND BACKGROUND

VynDAQel obtained the marketing authorization for the indication of “suppression of progression of peripheral neuropathy in transthyretin-type familial amyloid polyneuropathy” in September 2013. After an additional application for the indication of “transthyretin amyloid cardiomyopathy (hereinafter referred to as ATTR-CM)” was filed in November 2018, the approval for the additional application was obtained in March 2019.

VynDAQel is an orally available low molecular weight compound that binds to the thyroxine binding site of TTR and specifically stabilizes the TTR tetramers in plasma for both genetic variants and wild-type. This mechanism of action is expected to inhibit dissociation of the tetramers into monomers, which is a rate-limiting step in amyloid formation, suppress amyloid deposition in tissues such as the myocardium, and delay or deter the progression of ATTR-CM disease.

“VynDAQel Capsules Special Investigation - Investigation on patients with transthyretin amyloid cardiomyopathy -” (hereinafter referred to as this study) will be conducted to

*PFIZER CONFIDENTIAL*

*CT24-WI-JPN-GPSP01-RF09 7.0 Non-Interventional Study Protocol Template for Secondary Data Collection*

*Study 15-Sep-2022*

*Page 9 of 39*

comprehend information on the safety (e.g., onset status of adverse reactions), etc. of patients who are treated with Vyndaqel for the treatment of ATTR-CM.

Vynmac was approved for marketing in September 2021 for ATTR-CM because it demonstrated the same safety and tolerability as those of tafamidis meglumine 80 mg (20 mg x 4 capsules) containing the same physiologically active ingredient in patients with ATTR-CM. In this study, Vynmac is also investigated: when Vynmac is used during the observation period, observation will be also continued until the planned observation period is completed to comprehend information on the safety (e.g., onset status of adverse reactions), etc. of Vynmac.

This study shall be conducted in strict compliance with the “MHLW Ordinance on the Standard for Post-Marketing Studies and Clinical Trials of Medical Products” (MHLW Ordinance No. 171, dated December 20, 2004), the “Enforcement of the MHLW Ordinance on the Standard for Post-marketing Studies and Clinical Trials of Medical Products” (PFSB Notification No. 1220008, dated December 20, 2004), the “MHLW Ordinance on the Standard for Post-marketing Safety Control of Medical Products, Quasi-medical Products, Cosmetics, Medical Devices, and Regenerative Medical Products” (MHLW Ordinance No. 135, dated September 22, 2004), the “Enforcement of the MHLW Ordinance on the Standard for Post-marketing Safety Control of Medical Products, Quasi-medical Products, Cosmetics, Medical Devices, and Regenerative Medical Products” (PFSB Notification No. 0812-4, dated August 12, 2014), the “MHLW Ordinance to Partially Amend the MHLW Ordinance on the Standard for Post-marketing Studies and Clinical Trials of Medical Products” (MHLW Ordinance No. 116, dated October 26, 2017), and the “Announcement of the MHLW Ordinance to Partially Amend the MHLW Ordinance on the Standard for Post-marketing Studies and Clinical Trials of Medical Products” (Regarding the MHLW Ordinance on the Standard for Post-Marketing Studies and Clinical Trials of Medical Products) (PSEHB Notification No. 1026-1, dated October 26, 2017).

## 7. RESEARCH QUESTION AND OBJECTIVES

The objective of this study is to comprehend information on the long-term safety (e.g., onset status of adverse reactions), etc. of patients who are treated with Vyndaqel for the treatment of ATTR-CM after the approval for the indication of this drug for ATTR-CM was obtained. When Vynmac is used, the study will be also conducted to grasp information on safety (e.g., onset status of adverse reactions), etc. during the observation period.

[Conditions for approval for Vyndaqel]

Because the number of study participants in Japan is very limited, the background information of patients using this drug\* should be grasped by conducting a use-result survey in all patients while the data on a certain number of patients is accumulated after marketing and data on the safety and effectiveness of this drug should be collected early to take measures necessary for proper use of this drug.

\*: Vyndaqel

[Conditions for approval for Vynmac]

Because the number of study participants in Japan is very limited, the background information of patients using this drug\*\* or Vyndaqel Capsules 20 mg should be grasped by conducting a use-result survey in all patients while the data on a certain number of patients is accumulated after marketing and data on the safety and effectiveness of this drug or Vyndaqel Capsules 20 mg should be collected early to take measures necessary for proper use of this drug.

\*\* : Vynmac

### 7.1. Safety specifications

Important Potential Risks: Hepatotoxicity, hypersensitivity reactions, reproductive and developmental toxicity, infection, incorrect product selection between Vyndaqel and Vynmac

Important Missing Information: Safety in patients with severe hepatic impairment, administration to patients with variants

## 8. RESEARCH METHODS

### 8.1. Study design

This study is a multi-center cohort study of patients with ATTR-CM receiving Vyndaqel or Vynmac (hereinafter collectively referred to as this drug). The investigators complete the collection of case report forms (CRFs) based on the information extracted from the medical records created in daily medical practice.

### 8.2. Setting

Patients who satisfy all of the registration criteria are subject to this study.

#### 8.2.1. Registration criteria

Patients must meet all of the following inclusion criteria to be eligible for inclusion in the study:

- The purpose of treatment with this drug is ATTR-CM.

\*Patients who have participated in clinical studies of ATTR-CM and continue to receive treatment of ATTR-CM are eligible for inclusion.

Refer to the latest package insert of this drug for “indications” and “dosage and administration” when this drug is administered. The descriptions on ATTR-CM are excerpted and shown below:

**[Indication]**

Transthyretin amyloid cardiomyopathy (wild-type and variants-type)

**[Dosage and administration]**

Transthyretin amyloid cardiomyopathy

**<Vyndaqel Capsules 20 mg>**

The usual adult dose is 80 mg of tafamidis meglumine orally once daily. The dose may be decreased if not tolerated.

**<Vynmac Capsules 61 mg>**

The usual adult dose is 61 mg of tafamidis orally once daily.

**8.2.2. Exclusion criteria**

No exclusion criteria are set for this study.

**8.2.3. Study sites**

This study will be conducted at approximately 150 sites including the Departments of Cardiology, Department of Neurology, and Department of Internal Medicine, etc.

**8.2.4. Planned study period**

The planned period covered by this study is as follows.

Investigation period: March 2019 to September 2023 (From the start date of observation for the first subject to the end date of observation period for the last subject)

Registration period: March 2019 to March 2021 (From the start date of administration for the first subject to the start date of administration for the last subject)

However, CRFs may be collected when additional information needs to be collected.

**8.2.5. Study procedures**

**8.2.5.1. Study method**

All patients surveillance system: This study will be conducted with all patients surveillance system that all patients will be registered until data are collected on a target number of patients.

This study investigates patients who used a marketed product of this drug after the approval for the indication for ATTR-CM is obtained at contract sites. This study targets patients who used this drug until contracts are concluded with sites requested to conduct the study and also

includes patients who used this drug after the conclusion of contracts (including retrospective patients).

When additional information needs to be collected, the investigator shall complete a CRF upon request of the Sponsor (Pfizer Japan Inc., hereinafter the same). When a patient, whose CRF is to be collected, is transferred to another hospital during the observation period, the investigator shall inform the Sponsor of the name of the transferred medical institution. The Sponsor shall conclude a contract to conduct this study with the transferred medical institution and conduct the study there.

#### **8.2.6. Observation period**

[figure not shown]
30 months (Week 130) from the start of administration (Day 1)

However, for patients who discontinued this drug during the observation period, the observation period will be until the first visit after the date of discontinuation.

[figure not shown]
In this study, information will be collected using a booklet type CRF. Information during the following periods will be entered in each booklet.

If the patient is transferred to another hospital or department (hereinafter referred to as hospital transfer) during the observation period, the patient will be newly registered even at the transferred site and the CRF will be completed. If the patient is transferred to another hospital, the patient registration number of the original site will be conveyed to the transferred site. Although the patient will be given a new patient registration number at the transferred site at the time of registration, he or she will be determined to be a transferred patient by reporting the patient registration number of the original site and his/her data will be handled as the same patient. If the time point of 30 months after the start date of initial administration can be identified for the transferred patient, the observation period at the transferred site may be reset so that the total observation period of the patient in this study will become 30 months.

**Figure 1. Observation period for each booklet**

**Figure 2. Setting of observation period for transferred patients**

### 8.3. Variables

This study will be conducted according to the following schedule of observation.

For patients transferred from the clinical trial, the first administration day of a marketed product of this drug will be the first day of administration of this drug.

**Table 1. Variables and schedule of activities**

Variables	Registration form	Booklet 01		Booklet 02
		At start of administration of this drug	Start of administration to Month 12 (Week 52) of treatment	Week 53 to Month 30 (Week 130) of treatment
ID number	●	*1		
Gender	●	*1		
First day of treatment with this drug for ATTR-CM	●			
Confirmation of eligibility	●			
Identification of transferred patients	●	*1		
Usage experience of this drug	● *2	*1		
Birth year/age	● *3	*1		
Disease type of ATTR-CM	● *3	*1		
Severity of heart failure (NYHA Functional Classification)	● *3	*1	●	●
Inpatient/outpatient status		● *3		
Height/body weight		● *3		
Clinical laboratory test (serum albumin)		● *3		
Target disease		● *3		
Genotype of ATTR-CM (only for patients with variants)		● *3		
Presence/absence of liver/renal impairment, (only for liver impairment) severity		● *3		
Complication		● *3		
Presence/absence of pregnancy during the observation period (only for female patients)			●	●
Implementation status of the study and records at discontinuation			●	●
Confirmation of survival			●	●
Administration record of targeted drug			←→	←→
Concomitant therapy (Drug therapy/Device therapy)			←→	←→
Clinical laboratory tests			←→	←→
Adverse events			←→	←→
Obtaining consent for publication of results		←	←→	←→

\*1 While the contents of the registration form will be automatically reflected, the investigator will check the contents again and make corrections as necessary.

PFIZER CONFIDENTIAL

\*2 Not collected in the case of transferred patients.

\*3 Not collected if the patient is transferred to another hospital and the patient registration number of the original site is entered.

### 8.3.1. Patient characteristics

1. Enter the information at the start of administration of this drug into the registration form.

- a. Site information (if the study is conducted using paper CRFs)
- b. ID number
- c. Gender
- d. First day of treatment with this drug for ATTR-CM (first administration day of a marketed product of this drug for patients transferred from clinical trials, hereinafter the same)
- e. Identification of transferred patients (in the case of transferred patients, enter the patient registration number of the original site)
- f. Usage experience of this drug [administered this drug for the first time, transferred from clinical trials, or in treatment for transthyretin-type familial amyloid polyneuropathy (TTR-FAP) but also started to receive the treatment of ATTR-CM] (no entry is necessary for transferred patients)

If the patient is a transferred patient and the patient registration number of the original site has been entered, the entries for the following items g. to i. are not necessary (the entries are necessary even for the transferred patient if the patient registration number of the original site is not clear)

- g. Birth year (known at the start of administration of this drug) (if the birth year cannot be disclosed, enter the age at the start of administration of this drug)
  - h. Disease type of ATTR-CM (wild-type, variant, or unknown)
  - i. Severity of heart failure (NYHA Functional Classification)
2. The following will be recorded in CRF at the start of administration of this drug. If the contents of the registration form have been reflected, the investigator will check the contents again and make corrections as necessary.
- a. ID number
  - b. Gender

- c. Identification of transferred patients (in the case of transferred patients, enter the patient registration number of the original site)
- d. Usage experience of this drug (administered this drug for the first time, transferred from clinical trials, or in treatment for TTR-FAP but also started to receive the treatment of ATTR-CM) (no entry is necessary for transferred patients)

If the patient is a transferred patient and the patient registration number of the original site has been identified, the entries for the following items e. to o. are not necessary (the entries are necessary even for the transferred patient if the patient registration number is not clear)

- e. Birth year/age
- f. Inpatient/outpatient status
- g. Height (cm)
- h. Body weight (kg)
- i. Clinical laboratory test (serum albumin)
- j. Target disease
- k. Disease type of ATTR-CM (wild-type, variant, or unknown)
- l. Genotype of ATTR-CM (only for patients with variants)
- m. Severity of heart failure (NYHA Functional Classification)
- n. Presence/absence of liver impairment/renal impairment\*, (only for liver impairment) severity  
  
\*Liver impairment/renal impairment are not transient laboratory abnormalities but represent events that require clinical consideration and follow-up.
- o. Confirmation of complication [enter the names of chronic diseases including TTR-FAP (including allergy), diseases requiring treatment, diseases or disorders with sequelae, diseases that are cured after a certain post-treatment follow-up, and other diseases or syndromes which are considered problematic]

### 8.3.2. Administration record of targeted drugs

The following information will be recorded for the targeted products.

1. Drug name (Vyndaqel, Vynmac)

2. Daily dose
3. Number of doses per day
4. Treatment Period
5. Reason for change/washout

### **8.3.3. Concomitant therapy**

#### **8.3.3.1. Drug therapy**

For all drugs used during observation period, the following information should be recorded.

1. Drug name
2. Route of administration
3. Start date (the date entry is not necessary if the drug has been administered before the start of the study)
4. End date
5. Purpose of administration (for treatment of ATTR-CM, procedure for adverse events, or others)

#### **8.3.3.2. Non-drug therapy (device therapy)**

The presence or absence of device therapy during the observation period should be recorded. If the treatment is started during the observation period, the start date should be recorded (the date entry is not necessary if the drug has been administered before the start of the study).

1. Device therapy
2. Start date

### **8.3.4. Tests/clinical laboratory tests**

#### **8.3.4.1. Clinical laboratory tests**

The results of tests performed before the start date of administration (including the start date of administration) and during the observation period of each booklet (or until the first visit date after the date of discontinuation of this drug) should be recorded. If the abnormal value is clinically significant compared to the value before dosing, this information should also be recorded in detail in the adverse event field.

1. NT-proBNP
2. BNP

*PFIZER CONFIDENTIAL*

3. Troponin I

4. Troponin T

#### 8.3.4.2. Clinical symptoms

The following clinical symptoms should be recorded at the start of administration, Week 52, Week 130, and at the time of discontinuation.

- NYHA Functional Classification

**Table 2. NYHA Functional Classification\***

COPYRIGHTED MATERIAL

\*Excerpted from Guidelines for Diagnosis and Treatment of Acute and Chronic Heart Failure (2017 Revised Version)

#### 8.3.5. Presence or absence of pregnancy during the observation period (only for female patients)

The presence or absence of pregnancy at the end point of observation period in each booklet (or until the first visit date after the date of discontinuation of this drug) should be recorded. If pregnancy is found during the observation period, the information should be collected separately from the CRF.

#### 8.3.6. Implementation status of the study and records at discontinuation

The administration status of this drug at the end point of observation period in each booklet should be confirmed. If the patient discontinued the administration of this drug by the end point of observation period in each booklet, data at the first visit after the date of discontinuation should be recorded regardless of the reason for discontinuation. If the administration of this drug is continued, it should be entered as completed. If the administration is discontinued, only one of the following primary reasons should be selected. If the primary reason for discontinuation is an adverse event or others (abnormal laboratory test value), necessary information should be recorded in the adverse event field.

1. End date of the observation period (or the date of the first visit after the date of discontinuation)

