### 8.3.8. Adverse events

Occurrence of adverse events from the start date of administration of this drug to the end date of observation period (or first visit date after the date of discontinuation of this drug) should be confirmed and the following information should be recorded.

Also, further investigation should be separately conducted, if deemed necessary by Sponsor for patients who experienced a serious adverse reaction, an unexpected adverse reaction or other adverse reactions not listed in the package insert.

- Presence/absence of adverse event
- Name of adverse event
- Date of occurrence
- Seriousness
- Change in the administration of this drug
- Intervention
- Outcome

- Causal relationship to this drug

If the adverse event is associated with abnormal laboratory values, i.e., clinical laboratory tests, the following information should also be recorded.

- Name of laboratory test
- Site reference value
- Unit
- Date of measurement
- Test results

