#### Abnormal test findings

The criteria for determining whether an abnormal objective test finding should be reported as an AE are as follows:

- Test result is associated with accompanying symptoms, and/or
- Test result requires additional diagnostic testing or medical/surgical intervention, and/or
- Test result leads to a change in study dosing or discontinuation from the study, significant additional concomitant drug treatment, or other therapy, and/or
- Test result is considered to be an AE by the investigator or sponsor.

Merely repeating an abnormal test, in the absence of any of the above conditions, does not constitute an AE. Any abnormal test result that is determined to be an error does not require reporting as an AE.

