8.2.1.2. List of discontinuations and dropouts

For the safety analysis set and the efficacy analysis set, the number and proportion of discontinuations will be tabulated by timing [<12 months, ≥ 12 to <24 months, ≥ 24 to <30 months, ≥ 30 months]. In addition, the number and proportion of patients by reason for discontinuation will be tabulated.

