8.2.3.1.3. Details of adverse reactions

The number and proportion of patients with adverse reactions will be tabulated by SOC and PT for each of the following items:

- Seriousness [serious, non-serious]
- Number of days to onset [<26 weeks, \geq 26 weeks and <52 weeks, \geq 52 weeks and <78 weeks, \geq 78 weeks and <104 weeks, \geq 104 weeks and <130 weeks, \geq 130 weeks] (For the tabulation of incidence, the number of patients receiving at least one dose of this drug in each period category will be used as the denominator.)
- Action taken [suspended, dose reduced, dose increased, discontinued]

- Outcome [recovered/resolved, recovering/resolving, recovered/resolved with sequelae, not recovered/not resolved, fatal, unknown]

For outcomes, the number and proportion of patients with serious adverse reactions will be tabulated by SOC and PT.

If the same adverse reaction (of the same PT) occurs more than once in the same patient, it will be handled as follows in the tabulation of the number of patients with events:

- Seriousness: If both serious and non-serious events are reported, the event will be regarded as serious.
- Number of days to onset: Defined as the number of days to the first event.
- Action taken: If multiple types of actions were taken, one action will be adopted in the order of priority of discontinued, suspended or dose reduced, and other (none, dose increased).
- Outcome: The outcome of the last occurring event will be used.

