8.2.3.1.4. Safety specifications

For the safety specifications shown in Section 6.1, the number and proportion of patients will be tabulated. The number and proportion of patients with safety specifications will be tabulated by SOC and PT for each action taken and outcome.

In addition, safety specifications will be analyzed, taking into account the difference in exposure period, as described in Section 8.1.4.

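### A stop for an abnormal laboratory value can be coded 'Others' although the protocol defines it as an adverse event, so the only any-cause count of adverse-event discontinuations may be too low

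*Protocol*

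**What the plan says.** Protocol 8.3.6 asks for the status at the end of each booklet period. If the drug was stopped, "only one of the following primary reasons should be selected". The list that follows has separate entries for 'Adverse events' and 'Others'. The section then says: "If the primary reason for discontinuation is an adverse event or others (abnormal laboratory test value), necessary information should be recorded". The sentence goes on to name the place, so that for both reasons "necessary information should be recorded in the adverse event field".

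Protocol 10.4.1, under abnormal test findings, lists the conditions that make a test result reportable as an adverse event. One of them is: "Test result leads to a change in study dosing or discontinuation from the study".

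Protocol 8.3.8 lists what is recorded for each adverse event, including "Change in the administration of this drug" and the causal relationship. If the event involves an abnormal laboratory value, the test name, reference value, unit, date and result are also recorded.

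The SAP uses these fields in four places:
- Section 8.2.1.2, on disposition: "the number and proportion of patients by reason for discontinuation will be tabulated".
- Section 8.2.3.1.3 tabulates adverse reactions by action taken, with discontinued as one category. SAP 6.1 defines adverse reactions as events that the physician assessed as related.
- Section 8.2.3.1.4: "The number and proportion of patients with safety specifications will be tabulated by SOC and PT for each action taken and outcome". Hepatotoxicity is one of the safety specifications.
- Section 8.2.3.2.1 tabulates adverse events of any causality by seriousness, SOC and PT, without action taken.

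**The concern.** Two sections of the protocol class the same stop differently. Under 10.4.1 it is an adverse event. Under 8.3.6 it may sit under 'Others', and because only one reason is allowed, a patient entered there cannot also appear under 'Adverse events'. With about 150 sites planned (Protocol 8.2.3), uniform coding cannot be taken for granted.

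The share of patients who stop because of an adverse event is a basic tolerability figure, and the study's objective is long-term safety (Protocol 7). A reader of the final report will take it from the 'Adverse events' row of the reason table. If laboratory-driven stops are in the 'Others' row, that share is understated and nothing in the table shows it.

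**Working it through.** **Does a laboratory-driven stop always meet 10.4.1?** The condition in 10.4.1 names a change in dosing or discontinuation from the study, while 8.3.6 concerns stopping the drug. Stopping the drug is a change in dosing. Under Protocol 8.2.6 it also ends observation at the next visit. The condition is met on either limb.

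**Which planned outputs could count such a stop as a discontinuation for an adverse event?**

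| SAP output | Source field | Counts a laboratory stop coded 'Others'? |
|---|---|---|
| 8.2.1.2, reason for discontinuation | Reason (status) field | No |
| 8.2.3.1.3, adverse reactions by action taken | Adverse event field | Only if judged related |
| 8.2.3.1.4, safety specifications by action taken | Adverse event field | Only if the event is a safety specification; the section sits under the adverse reactions heading, so it may be limited to related events |
| 8.2.3.2.1, adverse events by seriousness | Adverse event field | Counts the event, not the stop |
| Section 9 listings | Adverse event field | Shows patients one by one, with no proportion |

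So the row in 8.2.1.2 is the only summary count of stops for adverse events regardless of causality. A laboratory-driven stop coded 'Others' and judged unrelated is not counted there. Nor does it reach the action-taken tables, unless 8.2.3.1.4 is read as covering all causalities and the event is a safety specification.

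**Direction.** A laboratory stop is entered under either 'Adverse events' or 'Others'. The first is consistent with 10.4.1. The second lowers the 'Adverse events' row. Coding of these stops cannot raise the row above the number that meet the definition.

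**Size.** The documents state no discontinuation rate, no share of stops due to laboratory values and no coding pattern, so there is no figure of the plan's own to reproduce on this point. The illustration below rests on assumptions alone. Let N = 300 (Protocol 8.5.1), d = the true share stopping for events that meet the adverse event definition, and s = the share of those stops coded 'Others'.

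Row count = N × d × (1 − s); row percentage = 100 × d × (1 − s).

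| d (patients) | s = 0 | s = 10% | s = 25% | s = 50% |
|---|---|---|---|---|
| 5% (15) | 15 (5%) | 13.5 (4.5%) | 11.25 (3.75%) | 7.5 (2.5%) |
| 10% (30) | 30 (10%) | 27 (9%) | 22.5 (7.5%) | 15 (5%) |
| 20% (60) | 60 (20%) | 54 (18%) | 45 (15%) | 30 (10%) |

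For example, 300 × 0.10 × (1 − 0.25) = 22.5. A count from the adverse event field by action taken stays at 15, 30 or 60 whatever s is, provided that field is completed as 8.3.6 requires.

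**The case against.** The strongest reply is that no safety event is lost. The instruction in 8.3.6 ends by sending laboratory stops to the adverse event field, where the event, its causality and the drug action are all recorded. Tables of adverse reactions, safety specifications and adverse events by seriousness do not depend on the reason code. Only one row of a disposition table can move, in a study that SAP 4 calls non-confirmatory and whose stated safety measure is the proportion with adverse reactions (Protocol 8.7). All of this stands, and it limits the point. It does not remove it, because no table uses the captured action to count stops of any causality.

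Three stronger readings are tempting, and the documents do not support them.

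- **A reader might infer that 8.3.6 orders the code 'Others'.** It presupposes that a laboratory stop may be entered there. An investigator applying 10.4.1 can select 'Adverse events', so an undercount is possible but not shown.
- **A reader might infer that hepatotoxicity suffers most.** The reason table is not split by event, and hepatotoxicity has its own action-taken table in SAP 8.2.3.1.4. The documents give no laboratory definition of it (SAP 6.1 refers to a separate document), and the tests listed in Protocol 8.3.4.1 are cardiac biomarkers.
- **A reader might turn the sample size rationale into a number of miscoded patients.** At 5.88%, 300 × 0.0588 = 17.64 hepatotoxicity cases are expected. If a quarter to a half stopped on laboratory values, that would be 4.4 to 8.8 patients. This needs an assumed stopping share and also the assumption that every such stop is coded 'Others'. With coding that follows 10.4.1 the number is zero. The plan's statement of about 98% probability for at least 10 cases reproduces (exact binomial 0.984), but it concerns incidence, not discontinuation, and is untouched.

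One caution about the remedy is also right. Protocol 10.4.1 lists lack of efficacy and disease progression as adverse events. Moving every patient with an adverse event and a stop into the 'Adverse events' row would override primary reasons such as insufficient effectiveness.

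**Conclusion.** The point holds in a limited form. Protocol 8.3.6 and 10.4.1 disagree on how to class a stop for an abnormal laboratory value. The 'Adverse events' row in SAP 8.2.1.2 can therefore be too low, and no other planned table supplies the any-causality count. The error for these stops runs one way. Its amount is unknown and possibly zero; it depends on how sites coded such stops, which the documents do not show. The conclusion assumes that the reason table is built from the status field, as its wording indicates. The defect is in one summary figure and does not extend to the capture of safety events.

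**What to change.** In SAP 8.2.1.2:

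1. Count under 'Adverse events' any patient with status 'Others' whose stop was for an abnormal laboratory value recorded as an adverse event with discontinuation as the change in administration. The laboratory details required by Protocol 8.3.8 help to identify these patients. Leave all other primary reasons as the investigator gave them, so the reasons stay mutually exclusive.
2. Add one line with the number and proportion of patients with any adverse event, regardless of causality, whose action taken was discontinuation. Show it beside the investigator's primary reasons, not in place of them, because it will include stops for lack of efficacy or progression that were recorded as adverse events.

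Reconcile the wording of Protocol 8.3.6 with 10.4.1. Observation was planned to end in September 2023 (Protocol 5), so this mainly serves the record. The SAP change is the one that corrects the reported figure.

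The cost is one extra derivation from fields already collected. The reported share stopping for adverse events may become slightly less favourable.
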